4.1.2 Investigational Product Dosing Regimen

Participants who meet entry criteria will be randomized 1:1:2 by the interactive voice/web response system (IxRS) to 1 of the 3 treatment sequences described in Section 4.1.

Figure 3 presents an overview of the IP that will be administered for each randomized treatment sequence.

Figure 3 Investigational Product Administered Q4W by Randomized Treatment Sequence

^a In the extension phase, participants will receive benralizumab on a Q8W or Q4W dosing regimen, as predetermined at randomization (Visit 2). Participants randomized to receive benralizumab Q8W in the extension phase will also receive placebo at intervening study visits when they are not receiving benralizumab.

Q4W, every 4 weeks; Q8W, every 8 weeks.

Dosing Regimen at Visits 2, 3, 4, and 5 (Initial 16-Week Double-blind Treatment Period)

All participants will receive randomized double-blind IP Q4W at Weeks 0, 4, 8, and 12 (Figure 3).

Dosing Regimen at Visits 6 Through EOT, Benralizumab 30 mg

At Week 16, participants initially randomized to benralizumab 30 mg will receive benralizumab 30 mg Q4W or Q8W according to their original randomization at Visit 2 (Week 0). Participants randomized to the Q8W regimen will receive placebo at the Week 16 visit and benralizumab 30 mg at the Week 20 visit, and will continue to alternate between these treatments Q4W until Week 48 (Figure 3).

Dosing Regimen at Visits 6 Through EOT, Placebo

At Weeks 16, 20, and 24, participants initially randomized to placebo will receive benralizumab 30 mg Q4W. At Week 28, these participants will transition to receive benralizumab 30 mg Q8W; they will receive placebo at the Week 28 visit and benralizumab 30 mg at the Week 32 visit, and will continue to alternate between these treatments Q4W until Week 48 (Figure 3).

The final dose of benralizumab or placebo will be administered at Week 48.

4.2 Scientific Rationale for Study Design

This is a Phase 2 study designed to evaluate the efficacy and safety of benralizumab in the treatment of patients with moderate to severe AD.

This study's inclusion/exclusion criteria and run-in period (including a 7-day washout of topical medications for AD) are designed to capture a population appropriate for treatment with benralizumab, which is patients with AD who remain symptomatic despite treatment with topical medications. Both patient-reported symptoms and histological findings (ie, eosinophil counts in biopsies) will be captured to ensure the patient population is appropriate for the study and to establish baseline measurements for determining clinical and PD treatment effect.

Loss of skin barrier function and increased severity of AD predisposes patients' skin to microbial colonization and chronic skin inflammation (Leung and Guttman-Yassky 2014). Potential subpopulations with more evident eosinophil-driven AD have been noted in the literature and include Staphylococcus aureus-colonized adult patients with more severe disease and a distinct phenotype (ie, elevated blood eosinophils, major basic protein, $\Box I$ in skin, eosinophil cell lysis by Staphylococcus aureus α -hemolysin increasing tissue injury) and children and adolescents, whose disease process is more inflammatory in nature and driven more so by the innate immune system (Simpson et al 2018). Therefore, this study will include minimum cohort sizes for both adults (\geq 18 years of age) and adolescents (\geq 12 to < 18 years

of age) and baseline blood eosinophil cohorts (< $300 \text{ versus} \ge 300$) to ensure a broad distribution of patients across these characteristics to enable exploration of potential responder populations.

The study's 16–week randomized, double-blind, placebo-controlled, parallel-group treatment period is designed to compare the efficacy and safety of benralizumab 30 mg with placebo. This design is considered appropriate for demonstrating efficacy and safety without bias in a clinical trial (Leshem et al 2019). The study treatment duration is considered appropriate for this disease and was based on the treatment duration for previous studies in patients with AD (Blauvelt et al 2017, Guttman-Yassky et al 2019, Simpson et al 2016, and Thaci et al 2016).

The primary endpoint chosen is the proportion of patients with a binary response of IGA 0/1 and a decrease of ≥ 2 points from baseline in IGA at Week 16. The IGA assesses the overall inflammatory signs of AD (erythema, induration/papulation, lichenification, oozing/crusting) and is recommended by international guidelines to be used in clinical practice to determine disease activity and response to treatment. It has also been used in clinical trials for the registration of other products for the treatment of AD. Additional secondary endpoints are included to provide a complete picture of the efficacy achieved with benralizumab treatment.

The 36-week extension period will provide an opportunity to evaluate long-term benralizumab treatment in patients with AD. The effect of benralizumab 30 mg Q8W as a maintenance dosing regimen will be compared with benralizumab 30 mg Q4W. Participants who received placebo during the initial 16 weeks of the study will switch to benralizumab 30 mg; these participants will receive 3 doses of benralizumab 30 mg Q4W followed by benralizumab 30 mg Q8W for the remainder of the extension period. This regimen has been included in the extension period to provide a preliminary evaluation of the efficacy and safety of the approved dosing regimen for patients with severe asthma, when administered to patients with AD.

4.3 Justification for Dose

The PK of benralizumab are well-characterized (Wang et al 2017), and benralizumab is expected to demonstrate consistent PK across different disease populations. The safety and tolerability of a range of doses of benralizumab have been demonstrated. In Phase 3 asthma studies, over 3500 patients have received benralizumab 30 mg. In Phase 2 and 3 studies in patients with chronic obstructive pulmonary disease, over 1100 patients have received benralizumab 100 mg. No dose-limiting safety issues have been identified with dosing in clinical studies up to 100 mg Q8W for 52 weeks (refer to the Investigator Brochure for details).

The approved dosing regimen of benralizumab in severe asthma is 30 mg Q4W for the first 3 doses, followed by 30 mg Q8W thereafter. In adult and adolescent patients with severe asthma (SIROCCO [Bleecker et al 2016] and CALIMA [FitzGerald et al 2016]), treatment with

benralizumab 30 mg Q8W and Q4W resulted in near complete blood eosinophil depletion for both the Q8W and Q4W dosing regimens. Since the PK/PD relationship of adolescents with asthma has been shown to be consistent with those of adults (SIROCCO and CALIMA) and given PK/PD relationships are consistent across disease populations, the same benralizumab treatment regimen will be administered to adults and adolescents in this study. Treatment with benralizumab 30 mg Q4W has also been shown to reduce blood and tissue eosinophilia in GI tissue of patients with varied clinical subtypes of HES where patients have higher blood eosinophils and significant organ manifestations of eosinophilic inflammation (Kuang et al 2019).

Based on results for the asthma studies, participants will receive benralizumab 30 mg or placebo Q4W during the initial 16-week treatment period. A 16-week treatment period was chosen based on previous studies in patients with AD (Simpson et al 2016) in order to maximize the chances of demonstrating efficacy. Participants will subsequently either transition to a 30 mg Q8W dosing regimen or remain on a 30 mg Q4W regimen during the blinded extension period to evaluate the effect of a Q8W maintenance dosing regimen relative to Q4W over the longer-term treatment period.

4.4 End of Study Definition

The end of study is defined as the last expected visit/contact of the last participant participating in the study.

A participant is considered to have completed the study when he/she has completed his/her last scheduled visit/telephone contact.

See Appendix A 6 for guidelines for the dissemination of study results.

5 STUDY POPULATION

Prospective approval of protocol deviations to inclusion or exclusion criteria, also known as protocol waivers or exemptions, is not permitted.

Each participant should meet all of the inclusion criteria and none of the exclusion criteria for this study in order to be randomized to IP. Under no circumstances can there be exceptions to this rule. Participants who do not meet the entry requirements are screen failures (Section 5.4).

In this protocol, "enrolled" is defined as a participant's agreement to participate in a clinical study following completion of the informed consent/assent process. "Randomized" participants are defined as those who undergo randomization and receive a randomization number.

For procedures for withdrawal of incorrectly enrolled participants, refer to Section 7.1.2.

5.1 Inclusion Criteria

Participants are eligible to be included in the study only if all of the following criteria apply:

Informed Consent/Assent/age/gender/weight

- 1 Provision of the signed and dated written informed consent/assent of the participant prior to any mandatory study-specific procedures, sampling, and analyses. The informed consent/assent process is described in Appendix A 3.
- 2 Male and female participants \geq 12 years of age at the time of signing the ICF.

Type of Patients and Disease

- 3 Physician-confirmed diagnosis of AD (according to American Academy of Dermatology Consensus Criteria) that is not adequately controlled with topical medications.
- 4 EASI score of \geq 12 at screening and \geq 16 at randomization.
- 5 IGA score of \ge 3 (on a scale of 0 to 4, in which 3 is moderate and 4 is severe) at screening and at randomization.
- 6 AD involvement of \geq 8% body-surface area at screening and \geq 10% body-surface area at randomization.
- 7 A pruritus numerical rating scale average score for maximum itch intensity of \geq 4, based on the average of daily pruritus numerical rating scale scores for maximum itch intensity reported during the 7 days prior to randomization.
- 8 Documented recent history (within 6 months prior to screening) of inadequate response to treatment with topical medications, or patients for whom topical treatments are otherwise medically inadvisable (eg, because of important side effects or safety risks).
- 9 Participants that have applied a stable dose of topical emollient (moisturizer) twice daily for \geq 7 consecutive days immediately before the randomization visit. (NOTE: See exclusion criterion 11 for limitations regarding emollients).
- 10 Participants must be willing and able to complete daily PRO assessments:
 - (a) Complete at least 70% of daily PRO assessments between Visit 1 and Visit 2 and
 - (b) Complete at least 5 of 7 daily PRO assessments in the 7 days prior to Visit 2.

Reproduction

11 Females of childbearing potential (FOCBP) must agree to use a highly effective method of birth control (confirmed by the Investigator) from randomization, throughout the study duration, and within 12 weeks after last dose of IP and have a negative serum pregnancy test result on Visit 1.

Highly effective methods of birth control (defined as those that can achieve a failure rate of less than 1% per year when used consistently and correctly) include:

- (a) Combined (estrogen and progestogen containing) hormonal contraception associated with inhibition of ovulation: oral, intravaginal, or transdermal.
- (b) Progestogen-only hormonal contraception associated with inhibition of ovulation: oral, injectable, or implantable.
- (c) Intrauterine device.
- (d) Intrauterine hormone-releasing system.
- (e) Bilateral tubal occlusion or ligation.
- (f) Sexual abstinence, ie, refraining from heterosexual intercourse (the reliability of sexual abstinence needs to be evaluated in relation to the duration of the clinical study and the preferred and usual lifestyle of the participant).
- (g) Vasectomized sexual partner (provided that partner is the sole sexual partner of the FOCBP study participant and that the vasectomized partner has received medical assessment of the surgical success).
- 12 Females not of childbearing potential are defined as females who are either permanently sterilized (hysterectomy, bilateral oophorectomy, or bilateral salpingectomy) or who are postmenopausal. Females will be considered postmenopausal if they have been amenorrheic for ≥ 12 months prior to the planned date of randomization without an alternative medical cause. The following age-specific requirements apply:
 - (a) Females < 50 years old will be considered postmenopausal if they have been amenorrheic for 12 months or more following cessation of exogenous hormonal treatment and with follicle-stimulating hormone (FSH) levels in the postmenopausal range. Until FSH is documented to be within menopausal range, the participant should be treated as a FOCBP.
 - (b) Females ≥ 50 years old will be considered postmenopausal if they have been amenorrheic for 12 months or more following cessation of all exogenous hormonal treatment.

5.2 Exclusion Criteria

Participants are excluded from the study if any of the following criteria apply:

Medical Conditions

- 1 Participants with active dermatological conditions (eg, psoriasis, seborrheic dermatitis, cutaneous lymphoma) other than AD that, in the investigator's opinion, may interfere with the study assessments.
- 2 Known active allergic or irritant contact dermatitis that, in the investigator's opinion, may interfere with the study assessments.
- 3 Current malignancy, or history of malignancy, with the exception of:

- (a) Participants who have had basal cell carcinoma, localized squamous cell carcinoma of the skin, or in situ carcinoma of the cervix are eligible provided that the participant is in remission and curative therapy was completed at least 12 months prior to the date informed consent/assent, was obtained.
- (b) Participants who have had other malignancies are eligible provided that the participant is in remission and curative therapy was completed at least 5 years prior to the date informed consent/assent, was obtained.
- 4 Any disorder, including, but not limited to, cardiovascular, gastrointestinal, hepatic, renal, neurological, musculoskeletal, infectious, endocrine, metabolic, hematological, psychiatric, or major physical impairment that is not stable in the opinion of the Investigator and could:
 - (a) Affect the safety of the participant throughout the study.
 - (b) Influence the findings of the studies or their interpretations.
 - (c) Impede the participant's ability to complete the entire duration of study.
- 5 History of anaphylaxis to any biologic therapy or vaccine.
- 6 A helminth parasitic infection diagnosed within 24 weeks prior to the date informed consent/assent is obtained that has not been treated with, or has failed to respond to standard of care therapy.
- 7 Any clinically significant abnormal findings in physical examination, vital signs, haematology, clinical chemistry, or urinalysis during screening/run-in period which, in the opinion of the Investigator, may put the participant at risk because of his/her participation in the study, or may influence the results of the study, or the participant's ability to complete entire duration of the study.
- 8 Current active liver disease:
 - (a) Chronic stable hepatitis B and C (including positive testing for hepatitis B surface antigen or hepatitis C antibody), or other stable chronic liver disease are acceptable if participant otherwise meets eligibility criteria. Stable chronic liver disease should generally be defined by the absence of ascites, encephalopathy, coagulopathy, hypoalbuminemia, esophageal or gastric varices, or persistent jaundice, or cirrhosis.
 - (b) Alanine aminotransferase (ALT) or aspartate aminotransferase (AST) level ≥ 3 times the upper limit of normal, confirmed by repeated testing during the run-in period. Transient increase of AST/ALT level that resolves by the time of randomization is acceptable if in the Investigator's opinion the participant does not have an active liver disease and meets other eligibility criteria.
- 9 A history of known immunodeficiency disorder including a positive human immunodeficiency virus (HIV) test.

Prior/concomitant Therapy

- 10 Participants who have received treatment for AD with TCS, topical calcineurin inhibitors (TCI), or topical phosphodiesterase-4 (PDE4) inhibitors within the 7 days prior to the randomization visit.
- 11 Initiation of treatment of AD with prescription moisturizers or moisturizers containing additives such as ceramide, hyaluronic acid, urea, or filaggrin degradation products during the screening period (patients may continue using stable doses of such moisturizers if initiated before the screening visit).
- 12 Regular use (2 visits per week) of a tanning booth/parlor or phototherapy for AD within 4 weeks prior to the randomization visit.
- 13 Use of immunosuppressive medication, including, but not limited to: methotrexate, cyclosporine, azathioprine, systemic corticosteroids within 4 weeks or 5 half-lives prior to the date informed consent/assent is obtained, whichever is longer.
- 14 Known history of allergy or reaction to any component of the IP formulation.

Other

- 15 Receipt of immunoglobulin or blood products within 30 days prior to the date informed consent/assent is obtained.
- 16 Receipt of any marketed or investigational biologic within 4 months or 5 half-lives prior to the date informed consent/assent is obtained, whichever is longer.
- 17 Receipt of live attenuated vaccines 30 days prior to first dose of IP.
- 18 Receipt of any investigational nonbiologic within 30 days or 5 half-lives prior to the date informed consent/assent is obtained, whichever is longer.
- 19 Previously received benralizumab (MEDI-563, FASENRA).
- 20 Change to allergen immunotherapy or new allergen immunotherapy within 30 days prior to the date of informed consent/assent and anticipated changes in immunotherapy throughout the study.
- 21 Planned elective major surgical procedures during the conduct of the study.
- 22 Previous randomization in the present study.
- 23 Concurrent enrollment in another clinical trial.
- 24 AstraZeneca staff involved in the planning and/or conduct of the study.
- 25 For females only: Currently pregnant, breastfeeding, or lactating females.
 - (a) A serum pregnancy test will be done for FOCBP at Visit 1 and a urine pregnancy test must be performed for FOCBP at each subsequent treatment visit prior to IP administration. A positive urine test result must be confirmed with a serum pregnancy test. If serum test is positive, the participant should be excluded.

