Overall, the AE profile in adolescents was generally similar to the overall population in Phase 3 studies conducted with benralizumab; few SAEs were reported for adolescent patients. Additionally, during the benralizumab Phase 3 asthma exacerbation studies, extensive evaluation of immunoglobulins and flow cytometric assessment of cell subtypes demonstrated no differences between adolescent patients receiving benralizumab compared with placebo. Of note, mepolizumab had an acceptable AE profile in children with eosinophilic esophagitis as young as 2 years, and the PK in children was similar to adults (Assa'ad et al 2011).

In summary, there have been no safety signals detected in previous clinical studies with benralizumab or other monoclonal antibodies (mepolizumab) that deplete eosinophils that would preclude administration of benralizumab to adolescent participants ≥ 12 years of age.

Serious hypersensitivity reactions (including anaphylaxis) are an identified risk of biologic therapy, including benralizumab. Anaphylaxis may be life-threatening. Risk minimization includes observation in line with clinical practice following IP administration for the appearance of any acute drug reactions. Refer to Appendix E for further information and guidance.

Serious infections have been reported for benralizumab. A relationship between eosinophil depletion and serious infection has not been established.

Development of anti-drug antibodies (ADA) to benralizumab has been documented. Potential risks of developing ADA include decreased drug efficacy and hypersensitivity reactions (eg, anaphylaxis or immune complex disease). To date, no confirmed cases of immune complex disease have been observed and no appearance of a relationship between ADA and treatmentemergent AEs has been established. There was no impact of ADA on overall benralizumab safety or efficacy in the previous Phase 3 studies in asthma.

Eosinophils are a prominent feature of the inflammatory response to helminthic parasitic infections, and the presence of infiltrating eosinophils has been circumstantially associated with a positive prognosis in certain solid tumors. Helminthic parasitic infections and malignancy will continue to be monitored as part of routine pharmacovigilance practices. (Refer to Section 5.2, exclusion criteria).

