2.3.3 Overall Benefit:Risk Conclusion

Given the clinical evidence to date to support the use of benralizumab 30 mg Q4W in eosinophilic diseases and the established PK, PD, and safety profile in adolescent and adult

patients with severe asthma, the benefit-risk assessment of the use of benralizumab for AD in adult and adolescent patients appears favorable. Data from the approved severe asthma indication demonstrate that benralizumab 30 mg Q4W is safe and well tolerated among adolescent patients, and treatment with placebo posed no serious risks in adolescent patients. The favorable benefit/risk assessment of benralizumab supports the inclusion of adolescents in this Phase 2 study.

Based on the extensive safety data already available, the benefit risk profile in patients with AD is expected to be commensurate with that observed in the benralizumab asthma pivotal trials. Risk minimization measures include exclusion of patients with allergy or reaction to any component of the IP formulation, untreated parasitic infection, a history of anaphylaxis to any biologic therapy, active or recent malignancy, and exclusion of pregnant females. Risk minimization measures will be maintained during the conduct of this study, in conjunction with the performance of AstraZeneca's routine pharmacovigilance activities.

An independent Data and Safety Monitoring Board (DSMB) will provide oversight, with particular focus on the adolescent participants, to ensure safe and ethical conduct of the study. The DSMB will have the responsibility of evaluating cumulative safety and other clinical trial data at regular intervals and making appropriate recommendations based on the available data. During the study, the benefit/risk assessment will be continuously monitored by the DSMB to ensure that the balance remains favorable. Refer to Appendix A 5 and the DSMB Charter for information regarding the independent DSMB.

Participants with AD in this Phase 2 study will be monitored for AEs throughout treatment with benralizumab or placebo and for 12 weeks following the last dose. This study will be conducted under applicable International Conference on Harmonisation Good Clinical Practice (GCP) Guidelines.

More detailed information about the known and expected benefits and risks and reasonably expected AEs of benralizumab may be found in the Investigator's Brochure.

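### Exclusion criterion 6 misses a known, unresolved helminth infection diagnosed more than 24 weeks before consent

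*Protocol*

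**What the plan says.** Protocol section 5.2, criterion 6, excludes "A helminth parasitic infection diagnosed within 24 weeks prior to the date informed consent/assent is obtained that has not been treated with", or that did not respond to, standard of care therapy. It is the only eligibility criterion that names helminth or parasitic infection.

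The reason for having it is in section 2.3.2: "Eosinophils are a prominent feature of the inflammatory response to helminthic parasitic infections". The same paragraph adds that "Helminthic parasitic infections and malignancy will continue to be monitored as part of routine pharmacovigilance practices" and sends the reader to section 5.2. Section 2.3.3 then summarizes the safeguards: "Risk minimization measures include exclusion of patients with allergy or reaction to any component of the IP formulation, untreated parasitic infection", followed by other items. No time limit is attached to the parasitic infection in that list.

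Malignancy, the other topic in that paragraph of section 2.3.2, is handled in criterion 3: "Current malignancy, or history of malignancy, with the exception of" two groups, both in remission. The second reads "Participants who have had other malignancies are eligible provided that the participant is in remission and curative therapy was completed at least 5 years" before consent.

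**The concern.** The hazard is an infection that is still present in a patient about to be given an eosinophil-depleting drug. Criterion 6 makes the decision depend partly on when that infection was diagnosed. Of two patients with the same known, untreated infection, one diagnosed 20 weeks before consent is excluded and one diagnosed 30 weeks before consent is not, at least by this criterion.

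What is at stake is participant safety. Adolescents are enrolled, and all three sequences are scheduled to receive benralizumab, because the placebo group switches at Week 16 (section 4.1.2). Section 5 allows no waivers of the criteria, so their literal wording carries weight.

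**Working it through.** No figure in the plan needs reproducing. The check is of the criterion's logic, followed by what else in the protocol could catch the missed case.

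**Step 1. Criterion 6 as a conjunction.** It applies when (A) the diagnosis falls within 24 weeks before consent and (B) the infection is untreated or refractory to standard care.

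- A true, B true: excluded.
- A true, B false (recent, successfully treated): not excluded.
- A false, B false (older, successfully treated): not excluded.
- A false, B true (older, still untreated or refractory): not excluded. This is the gap.

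**Step 2. Where the window sits relative to randomization.** Consent is at Visit 1, *r* weeks before randomization, with *r* from 1 to 4 (Table 3). The window therefore runs from 24 + *r* to *r* weeks before randomization:

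- *r* = 1: 25 to 1 weeks
- *r* = 2: 26 to 2 weeks
- *r* = 3: 27 to 3 weeks
- *r* = 4: 28 to 4 weeks

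Diagnoses made earlier than 25 to 28 weeks before randomization fall outside it. Read literally, so do those made in the last 1 to 4 weeks. This locates the gap; it does not size a risk.

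**Step 3. What else could catch the missed patient.**

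- Criterion 4 lists infectious disorders with no date limit, but requires that the Investigator consider the disorder unstable and that it could affect safety, findings or completion.
- Criterion 7 covers abnormal findings during screening and run-in, again subject to Investigator opinion.
- Table 3 repeats the eligibility review at Visit 2. That reaches into the run-in, but it applies the same criteria.
- Section 6.1.1 requires a check for contraindications before every dose, including the first. Section 6.1.2 withholds a dose when there are signs of a clinically significant infection.
- Section 7.1 lets the Investigator or sponsor stop treatment for risk, and the Investigator for an adverse event that contraindicates dosing. Its one helminth-specific ground needs an infestation that develops and leads to hospitalization.

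A quiet, long-standing infection could pass all of these: it may be judged stable, show no signs, and not be a new development.

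**Step 4. Comparison with criterion 3.** Current malignancy is excluded whatever its date, and the 12-month and 5-year limits apply only to patients in remission. Criterion 6 places its limit on unresolved disease. Nothing obliges the two criteria to match, but the comparison shows that the protocol elsewhere separates current disease from past disease.

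**The case against.** The best defence is that the patient is not unprotected. Criterion 4 fits a known infection that has failed therapy quite naturally, eligibility is reviewed again at Visit 2, and the hold in section 6.1.2 for signs of significant infection is not worded as opinion alone. This stands in part. It rules out saying that such patients would simply be enrolled and dosed. It does not supply a rule that names the infection and applies whatever the date.

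A reader might also infer that section 2.3.3 contradicts criterion 6, because it mentions untreated parasitic infection without a window. The document does not support that. The sentence is a summary which shortens other criteria too: it omits the malignancy time limits and the vaccine part of criterion 5. It is supporting context only.

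Nor does the protocol show demonstrated harm. Section 2.3.2 states that a link between eosinophil depletion and serious infection is not established. The concern is plausible in mechanism and no more.

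Finally, the window has a proper use: it spares a patient with a remote, never-treated infection that has since cleared. Simply deleting it would be wrong. Replacing it with an activity condition alone would admit a recently diagnosed, never-treated patient thought to have cleared, whom the present text excludes. Both points stand and shape the fix.

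**Conclusion.** Criterion 6 leaves a real but narrow gap. It does not exclude a known, unresolved helminth infection diagnosed more than 24 weeks before consent or, on a literal reading, one first diagnosed in run-in. Other provisions give cover that rests largely on Investigator judgement.

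The number affected is probably very small. That is an assumption, since the protocol gives no prevalence and no count can be derived. The point concerns known infections only and is not a call for helminth testing. It does not touch the efficacy endpoints, the analysis or the power. It is a cheap, optional improvement in wording for participant safety.

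**What to change.** Keep criterion 6 as it stands and add a second limb, for example: *or any known active (unresolved) helminth infection at randomization, irrespective of when it was diagnosed, for which standard of care has not been given or has not worked*. The style matches terms already used in criterion 2 ("Known active allergic or irritant contact dermatitis that") and criterion 8 ("Current active liver disease"). Because the limb is added, every patient now excluded stays excluded, and a remote infection that has cleared remains acceptable. Section 2.3.3 needs no change.

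The cost is one line of text and no added test. A very small number of patients with a known long-standing active infection would be kept out until treated; section 5.4.1 allows one re-screen with study physician approval. Whether an infection is active would be judged from history and existing results, so some judgement remains, but it would be directed at the right question.
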